6.2.4 Surveillance for SARS-CoV-2 Infection

In concert with the collection of adverse events, at each visit study subjects will be interviewed for potential symptoms of COVID-19 disease, recent diagnosis of SARS-CoV-2 infection or COVID-19, and for potential exposure to confirmed COVID-19 or confirmed SARS-CoV-2 infection from household/intimate contacts. A standardized question list will be used for this process.

Potential symptoms of COVID-19 disease include (at a minimum): fever, chills, cough, shortness of breath or difficulty breathing, fatigue, muscle or body aches, headache, new loss of taste or smell, sore throat, congestion or runny nose, nausea and diarrhoea.

Subjects should be reminded to contact the site within 24 hours if experiencing COVID-19-like symptoms or if exposed to a confirmed COVID-19 case.

Should a subject describe any of the following, or exposure to a confirmed case of COVID-19, the subject should receive a SARS-CoV-2 PCR test preferably within 72 hours (and repeated if clinically appropriate) to determine if he/she is positive for SARS-CoV-2 virus infection.

- TWO of the following systemic symptoms:
 - If onset is not within 48 hours after injection with Study Drug: fever ($\geq 38^{\circ}\text{C}$), chills, myalgia, headache, congestion or runny nose, nausea, diarrhoea
 - With onset at any time: sore throat, new olfactory and taste disorder(s)

OR

- ONE of the following respiratory signs/symptoms: cough, shortness of breath or difficulty breathing

OR

- Clinical or radiographical evidence of pneumonia

For subjects who terminate early from the study, the site will remind the subject to contact the site until 1 year post last dose of ARCT-021 if they experience any of the above symptoms of COVID-19 or if they receive a diagnosis of COVID-19 or SARS-CoV-2 infection (Section 3.9). If a subject reports symptoms of COVID-19, the Investigator will make reasonable efforts to perform a SARS-CoV-2 PCR test preferably within 72 hours to confirm diagnosis.

Reporting requirements for confirmed COVID-19 are described in Section 9.5.5

6.3 Restriction on the Lifestyle of Subjects

6.3.1 Contraception Requirements

All male subjects and women of childbearing potential (WOCBP) must refrain from sperm/egg donation and use highly effective contraception from the time of signing the informed consent form until at least 56 days after their last dose of Study Drug.

For male subjects engaged in sexual relations with a WOCBP either the subject or their female partner must use highly effective contraception from the time of signing the informed consent until 56 days after the subject's last dose of study treatment.

For the purposes of this study, WOCBP are defined as any female who has experienced menarche, and who does not meet one of the following conditions:

- Postmenopausal: 12 months of spontaneous amenorrhea in females > 55 years of age or, in females ≤ 55 years, 12 months of spontaneous amenorrhea without an alternative medical cause and FSH levels in the postmenopausal range for the laboratory involved
- 6 weeks after surgical bilateral oophorectomy with or without hysterectomy
- Post hysterectomy

For the purposes of the study, highly effective contraception is defined as follows:

For male subjects:

- Highly effective male contraception includes a vasectomy with negative semen analysis at follow-up, or the non-pregnant female partner of WOCBP uses a highly effective contraceptive method (defined below)
- Male subjects with partners that are pregnant must use condoms until at least 56 days after the last dose of Study Drug to ensure that the fetus is not exposed to the Study Drug

For female subjects and female partners of male subjects, highly effective female contraception methods comprise:

- Surgical sterilization (e.g., bilateral tubal occlusion), hormonal contraception associated with inhibition of ovulation (combined estrogen and progestogen containing, or progestogen-only), intrauterine contraception device or intrauterine hormone-releasing system (IUS).

Note: A female condom and a male condom should not be used together as friction between the two can result in either or both products failing.

7 STUDY DRUG

For additional information please refer to the Pharmacy Manual.

7.1 Study Drug Description

The Study Drug is ARCT-021.

ARCT-021 is presented as a sterile, frozen, aqueous formulation with 0.2 mg/mL of mRNA-2002 and as a 1 mL fill (0.2 mg/1 mL) in 2-mL Type I glass vials which must be stored frozen at -70°C (+/- 10°C). ARCT-021 is a white to off-white liquid when thawed with a nominal [REDACTED] and osmolality of approximately [REDACTED] mOsm/kg.

Table 3: ARCT-021 Characteristics

Strength	0.2 mg/ mL
Volume/Formulation	2.0 mL solution per vial
Route of Administration	IM*

*IM = intramuscular

7.2 Packaging and Labeling

The Sponsor will provide the Investigator with packaged ARCT-021 labeled in accordance with specific country regulatory requirements.

7.3 Study Drug Accountability

The study staff is required to document the receipt, dispensing, and return/destruction ARCT-021 supplies provided by the Sponsor. The Study Center must return all unused frozen vials of ARCT-021 to the Sponsor or designee. Used or thawed vials of ARCT-021 should be destroyed by the Study Center after drug accountability has been done by the unblinded study monitor.

8 TREATMENT OF SUBJECTS

8.1 Treatment Precautions

Adrenaline for subcutaneous injection, diphenhydramine for intravenous injection, and any other medications and resuscitation equipment for the emergency management of anaphylactic reactions must be available in close proximity in the room where the injection is being performed.

8.2 Study Drug Preparation

Please refer to the Pharmacy Manual provided by the Sponsor or designee for more detailed instructions for Study Drug preparation.

ARCT-021 (1 volume) must be diluted with 3 volumes of sterile water for injection (SWFI) to target an osmolality of approximately █ mOsm/kg. 0.9% sterile saline should then be added to reach the final target volume as shown in [Table 4](#). Following dilution, 0.5 mL of diluted ARCT-021 should be drawn up into a 1.0 mL syringe for administration. The syringe of ARCT-021 can be stored at room temperature ($\leq 25^{\circ}\text{C}$) but must be administered within 6 hours of first puncture of the drug vial.

Table 4. Dilution Volumes for Preparation of ARCT-021

Dose Level (mg)	Amount of ARCT-021 (mg)	Volume of ARCT-021 (mL)	Volume of SWFI (mL)	Volume of 0.9% Sterile Saline (mL)	Final Volume (mL)	Final Concentration (mg/mL)
7.5	150	0.75	2.25	7.0	10.0	15.0

Note: ARCT-021 must first be added to the empty vial provided by the Sponsor and then the SWFI added to the ARCT-021, followed by 0.9% sterile saline.

8.3 Study Drug Administration

Study Drug will be administered by injection into the lateral aspect of the deltoid muscle of the non-dominant arm.

Subjects should remain at the center for at least 30 minutes for observation following vaccine administration.

Epinephrine for subcutaneous injection, diphenhydramine for intravenous injection, and any other medications and resuscitation equipment for the emergency management of anaphylactic reactions must be available in close proximity in the room where the vaccination is administered.

If the subject experiences a severe reaction following vaccine administration, the CRO Medical Monitor should be contacted as soon as feasible to discuss if additional assessments may be clinically warranted prior to the discharge of the subject from the study center.

8.4 Other Protocol-Required Treatment Procedures

None

8.5 Safety Monitoring Rules

Clinical safety parameters, including laboratory tests and vital signs will be monitored throughout the study.

Confirmation Guidance: At any time during the study (Study Drug Administration or Post-Treatment Periods), clinical laboratory results that are \geq Grade 3 in severity or liver chemistry tests that meet the criteria presented below **must be confirmed** by performing measurements (ideally in the same laboratory that performed the initial measurement) on new specimens. All new specimen collections should take place as soon as possible (ideally within 3 days of the initial collection). For laboratory results that meet stopping rules, if the initial laboratory result is

observed during the Study Drug Administration Period, the results from the retest must be available prior to administering the next dose of Study Drug.

8.5.1 Safety Monitoring Rules for Liver Chemistry Tests

The following rules are adapted from the guidance for industry, “Drug-Induced Liver Injury: Premarketing Clinical Evaluation,” issued by the U.S. Department of Health and Human Services, Food and Drug Administration, July 2009.

In the event of an ALT or AST measurement that is $>3 \times$ ULN at any time during the study, the initial measurement(s) should be confirmed as described above. Additional, confirmatory measurements should also be performed if ALT or AST levels increase to $5 \times$ ULN.

Frequency of Repeat Measurements: Subjects with confirmed ALT or AST levels $> 3 \times$ ULN should have their liver chemistry tests (ALT, AST, ALP, INR, and total bilirubin) retested at least once-weekly until ALT and AST levels become $\leq 1.2 \times$ ULN or until clinically stable and/or an alternate underlying etiology is identified.

Further Investigation into Liver Chemistry Elevations: For subjects with confirmed ALT or AST levels $> 3 \times$ ULN, the following evaluations should be performed (these tests may be performed in local lab):

1. Obtain a more detailed history of symptoms and prior and concurrent diseases
2. Obtain further history for concomitant drug use (including nonprescription medications, herbal and dietary supplement preparations), alcohol use, recreational drug use, and special diets
3. Obtain a history for exposure to environmental chemical agents and travel
4. Serology for viral hepatitis (HAV IgM, HBsAg, HCV antibody, CMV IgM, and EBV antibody panel)
5. Serology for autoimmune hepatitis (e.g., antinuclear antibody (ANA))

Additional liver evaluations, including gastroenterology/hepatology consultations, hepatic CT or MRI scans, may be performed at the discretion of the Investigator, or if requested by the Sponsor Medical Monitor. Repetition of the above evaluations should be considered if a subject’s ALT and/or AST levels reach $5 \times$ ULN.

8.5.2 Safety Monitoring Rules for Local and Systemic Reactogenic Events

Monitoring and recording of solicited reactogenic adverse events will be performed according to Section [6.2.1](#) and [Appendix 1](#).

8.6 Treatment Stopping Rules for Individual Subjects

As subjects in this study receive a single dose administration of ARCT-021, stopping rules for subsequent doses of study vaccine do not apply.

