Treatment Groups	No separate groups are defined for this study. However, results may be analyzed by age group (≤ 55 years and > 55 years) and cumulative dose of ARCT-021 received. Additional sub-group evaluations may be defined and will be described in the statistical analysis plan.
Study Drug Dosage and Administration	
Subjects who received placebo and subjects who received a single injection of ARCT-021 in the Parent Study and are seronegative for SARS-CoV-2 neutralising antibodies at screening will receive ARCT-021 in this study at a 7.5 μg dose level.
 
Subjects who received two injections of ARCT-021 in the Parent Study will not receive any further injections of ARCT-021 in this study.
 
ARCT-021 will be administered by IM injection into the lateral aspect of the deltoid muscle of the non-dominant arm. Subjects should remain at the center for at least 30 minutes for observation following vaccine administration.
 
Epinephrine for subcutaneous injection, diphenhydramine for intravenous injection, and any other medications and resuscitation equipment for the emergency management of anaphylactic reactions must be available in close proximity in the room where the vaccination is administered.

Rationale for Dose and Schedule Selection	The dose level of ARCT-021 selected for use in this study (7.5 μ g) is based on the safety, tolerability, immunogenicity and T-cell response results observed in younger and older adults in Study ARCT-021-01. These results suggest single dose 7.5 μ g ARCT-021 administration has a favorable safety profile, binding and neutralising antibody response, and T-cell immune response following single dose administration to both younger and older adults.
Adjustment of Dose	Adjustment of dose is not permitted.
Study Stopping Criteria	As this is an extension study to determine long-term safety there are no study stopping criteria for the study.

	
Stopping rules for dosing of individual subjects are found in Section 8.6

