2.6 Risk:Benefit Assessment

2.6.1 Potential Risks

For a full discussion of the potential risks associated with ARCT-021 treatment please refer to the Guidance for the Investigator section of the Investigators' Brochure. A summary of the potential risks of treatment with ARCT-021, together with potential mitigation for these risks is shown in [Table 2](#). Study ARCT-021-02 has been designed with appropriate exclusion criteria, guidance for study vaccine discontinuation for individual subjects (Section 8.6), dose escalation and safety monitoring rules and ongoing review of safety data in order to minimize potential risks to study subjects. Overall, the risk to healthy volunteers is minimal.

Table 2: Potential Safety Considerations for Clinical Trial ARCT-021-02

Potential Safety Consideration	Basis for Consideration	Mitigation
Local and Systemic Reactogenicity	Vaccines are commonly associated with local inflammatory reactions at the injection site and systemic constitutional reactions due to immune stimulation. RNA based vaccines have a similar profile to other vaccine platforms (Bahl 2017 ; Feldman 2019 ; Crosby 2019 ; Morse 2010). Data from the GLP two and three dose local tolerability/reactogenicity toxicity studies with ARCT-021 in rabbits indicate that ARCT-021 was associated with transient elevation of some cytokines and CRP but	
It is not possible to completely mitigate against these reactions for the first administration of study vaccine since immune stimulation is essential for development of reactive immunity to the vaccine antigens. However, vaccination via the IM route results in a lower rate of local reactions than intradermal (I.D.) or subcutaneous (S.C) injection (Zhang 2015).Reactions can be treated symptomatically with ibuprofen or acetaminophen, as indicated. Severe effects can be treated with corticosteroids as indicated. Resuscitation equipment must be

Potential Safety Consideration	Basis for Consideration	Mitigation

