	
was well tolerated without any adverse effects on clinical observations, body weight, body temperature, food consumption, organ weight, or macroscopic pathology or histopathology. All local reactions (eschar, erythema, and edema) have been transient and most mild to moderate, with one moderate to severe. There was no worsening of local reactions with repeated administration. There have been no abnormalities suggestive of significant systemic reactions on gross observations.
	
available in the room where Study Drug is administered (Section 8.1).
 
 For solicited adverse events that are grade 3, anaphylaxis or unexpected systemic hypersensitivity reactions, subsequent doses of study vaccine will not be administered (Section Error! Reference source not found.). Local and systemic reactions will be proactively elicited in order to characterise the profile of ARCT-021 (Section 8.5.2). All dose levels evaluated in this study will already have been assessed in the Parent Study
Hepatic Events	
Liver is a target organ for LNPs such as those used in ARCT-021 and elevated transaminases have been observed in animal and human studies of other LNPs. Data from the GLP two and three dose local tolerability/reactogenicity toxicity studies with ARCT-021 in rabbits indicates that repeated administration of ARCT-021 was well tolerated without any adverse effects on hepatic enzymes or histopathology.
	
 AST, ALT, ALP and bilirubin will be monitored up to 28 days after the last administration of Study Drug (Appendix 1). Dose pause and stopping rules for hepatic enzymes are included in the clinical study protocol (Sections 8.5.1 and Error! Reference source not found.) All dose levels evaluated in this study will already have been assessed in the Parent Study

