3.10 Study Stopping Criteria

As this is an extension study to determine long-term safety there are no stopping criteria for the study.

Stopping rules for dosing of individual subjects are found in Section [8.6](#)

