5.2 Exclusion Criteria

1. Significant (as determined by Principal Investigator) noncompliance with the study visits or procedures in Study ARCT-021-01
2. Any subject that received placebo in the Parent Study and who is not willing to receive ARCT-021 in this study.

Only for subjects that will receive ARCT-021 in this study:

- 3 Receipt of any other SARS CoV-2 or other experimental coronavirus vaccine since completion of the Parent Study or planned during this study.

4. Diagnosis of new clinically significant abnormalities in medical history or physical examination since enrolment in the Parent Study, including but not limited to:
 - Respiratory disease (e.g., chronic obstructive pulmonary disease [COPD], asthma) requiring daily medications or oxygen currently or any treatment of respiratory disease exacerbations (e.g., COPD or asthma exacerbation) warranting hospitalization or an emergency room visit or supplemental oxygen.
 - Significant cardiovascular disease (e.g., congestive heart failure, cardiomyopathy, ischemic heart disease), myocarditis or pericarditis.
 - Neurological or neurodevelopmental conditions (e.g., migraines, epilepsy, stroke, seizures, encephalopathy, focal neurologic deficits, Guillain-Barré syndrome, encephalomyelitis or transverse myelitis).
 - New diagnosis of a significant hematologic abnormality (e.g., sickle cell disease, beta thalassemia)
 - New Diagnosis of autoimmune disease as listed by the American Autoimmune Related Disease Association ([Appendix 3](#))
 - Major surgery
5. Screening laboratory results as follows, or any other clinically significant abnormalities in screening laboratory values that would render a subject unsuitable for inclusion
 - ALT, AST, GGT, total bilirubin or alkaline phosphatase, > ULN unless approved by Sponsor Medical Monitor (or designee).
 - Hb <10 g/dL for females and <12 g/dL for males
 - Platelet count < 100x10⁹/L
 - eGFR < 50 ml/min/1.73m² calculated by Modification to Diet in Renal Disease [MDRD] study equation, unless approved by the Sponsor Medical Monitor (or designee)
6. Diabetes that is not, in the opinion of the investigator, adequately controlled with diet +/- antidiabetic medication
7. Use of any prescription or over-the-counter medications within 7 days prior to vaccination, unless approved by the Sponsor Medical Monitor (or designee).
8. Received immunoglobulins and/or any blood or blood products since completion of the Parent Study.

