9.4.3 Non-Serious Adverse Events

For subjects who receive ARCT-021 in this study and who did not receive ARCT-021 in the Parent Study, the recording of non-serious AEs will begin after the subject has received ARCT-021 and will stop 28 days after the last dose of ARCT-021, with the exception of ongoing adverse events that worsen in severity and/or become serious, which will continue to be recorded. AEs that occur prior to administration of ARCT-021, including those that occurred between leaving the Parent Study and dosing in this Study will be recorded as medical history.

For subjects who receive ARCT-021 in this study and who also received ARCT-021 in the Parent Study, the recording of non-serious AEs will begin from the time the subject received ARCT-021 in the Parent Study and will stop 28 days after the dose of ARCT-021 in this study, with the exception of ongoing adverse events that worsen in severity and/or become serious, which will continue to be recorded. Any AEs that occurred between leaving the Parent Study and entering this study will be recorded as AEs.

For subjects who do not receive ARCT-021 in this study, only medically attended non-serious events will be recorded as described above (Section 9.4.2). The Investigator will monitor each subject closely and record all observed or volunteered AEs in the EDC.

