10.2 Populations

Safety Population: All subjects who receive Study Drug in ARCT-021-02 only

Longitudinal Safety Population: All subjects who receive Study Drug in either ARCT-021-01 or ARCT-021-02

Immunogenicity Population: All subjects who receive Study Drug in either ARCT-021-01 or ARCT-021-02 and who have evaluable immunogenicity data following first vaccine administration.

Additional populations may be defined for individual immunogenicity endpoints and will be pre-specified in the SAP.

Within these populations, analyses will also include Cohorts that combine relevant safety and immunogenicity assessments across ARCT-021-01 and ARCT-021-02 according to time since administration of last dose of ARCT-021 (See [Table 5](#)). These cohorts are defined as follows.

Two primary cohorts will be defined:

- Cohort 1: ARCT-021-02 vaccinated participants (those participants who receive ARCT-021 in Study ARCT-021-02, including those who were assigned to receive placebo in the parent study (ARCT-021-01) and those who enter the ARCT-021-02 without detectable neutralising antibody responses at baseline)
 - This cohort will be further subdivided for an exploratory analysis of cohorts:
 - Cohort 1a: Primary vaccination (Those participants whose first ARCT-021 vaccine administration occurs in the ARCT-021-02 study) and
 - Cohort 1b: Booster vaccination (Those participants who received primary vaccination in the ARCT-021-01 study and who receive an additional dose of ARCT-021 in the ARCT-021-02 study)
- Cohort 2: ARCT-021-01 vaccinated participants (those participants who were vaccinated with ARCT-021 in the parent study and who do not receive subsequent vaccination with ARCT-021 in the current extension study).
 - This cohort will be further subdivided for an exploratory analysis of subcohorts:
 - Cohort 2a: Those participants who received ARCT-021 7.5 µg dose as a single dose administration in the parent study (Cohorts D1 and D2)
 - Cohort 2b: Those participants who received ARCT-021 10.0 µg dose as a single dose administration in the parent study (Cohort C)
 - Cohort 2c: Those participants who received alternate doses and schedules of ARCT-021 in the parent study (Cohorts A, B)
 - Cohort 2d: Those participants who receive two-dose schedules of ARCT-021 in the parent study (Cohorts E, F, G, H)

Additional analysis cohorts, if required, will be prespecified in the statistical analysis plan.

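### The single-dose reason for having no individual stopping rule does not fit Cohort 1b, already dosed in the parent study, and no eligibility criterion names a prior reaction to ARCT-021

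*Protocol*

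**What the plan says.** - **Protocol Table 2 (Section 2.6.1)**, in both the reactogenicity row and the pro-inflammatory row: "For solicited adverse events that are grade 3, anaphylaxis or unexpected systemic hypersensitivity reactions, subsequent doses of study vaccine will not be administered". The cross-reference that follows is broken in both rows.
- **Protocol 2.6.1** counts, among the features that keep risk low, "guidance for study vaccine discontinuation for individual subjects (Section 8.6").
- **Protocol 3.10** and the **synopsis** (Study Stopping Criteria) send the reader to the same place. The synopsis puts it as "Stopping rules for dosing of individual subjects are found in Section 8.6".
- **Protocol 8.6** contains no rule. Because each subject receives one dose in this study, "stopping rules for subsequent doses of study vaccine do not apply".
- **Protocol 10.2** defines Cohort 1b as those "who received primary vaccination in the ARCT-021-01 study and who receive an additional dose of ARCT-021" in this study. Section 9.4.3 treats the two doses as one exposure history: for these subjects, "the recording of non-serious AEs will begin from the time the subject received ARCT-021 in the Parent Study".
- **Protocol 3.2** makes dosing the default for single-dose parent-study subjects who are seronegative at screening.

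**The concern.** The risk section tells an ethics committee or investigator that certain reactions stop further dosing, and that Section 8.6 gives the detail. Section 8.6 gives none, and the reason it offers describes only part of the dosed population. For a Cohort 1b subject the injection in this study is a second exposure to ARCT-021.

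At stake is whether someone who had a grade 3 solicited reaction to the parent dose, since resolved, should be dosed again. A site working from Sections 5 and 8.6 finds no rule on this and has to decide case by case. If it withholds the dose, the protocol does not say what follow-up that subject then has.

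**Working it through.** No arithmetic is stated in the plan on this point. The check sets the texts side by side.

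**1. What Table 2 probably meant.** The bullets look like remnants of a two-injection schedule. Their cross-references are broken. Section 6.2.1 still describes diary reviews for a second injection at Days 36 and 43. Section 2.6.1 still mentions dose escalation. The summary of changes in Appendix 4 records that 8.6.1 to 8.6.3 were taken out when the study became single-dose. The likely original target was a second injection within this study.

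**2. Whom the 8.6 reason covers.** Count ARCT-021 injections per subject:
- Cohort 1a: 0 in the parent study + 1 here = 1. No earlier dose exists to react to, so the reason holds.
- Cohort 1b: 1 in the parent study + 1 here = 2. The dose here is a subsequent dose, so the reason fails.

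**3. Whether another control fills the gap.**
- Inclusion 2 requires completion of the parent study. A subject whose grade 3 reaction resolved can meet it.
- Inclusion 4 (healthy) and exclusion 14 (any other unsuitable condition) rest on the opinion of the Investigator or, for exclusion 14, the Sponsor.
- Exclusion 4 covers "Diagnosis of new clinically significant abnormalities in medical history or physical examination since enrolment in the Parent Study". Its list is open-ended and its period spans the parent dose, so it could plausibly catch anaphylaxis. Its examples are diseases and major surgery, not a resolved grade 3 fever or myalgia.
- The retest rule in 8.5 concerns laboratory results.
- Section 8.7.1 concerns acute illness or fever within 72 hours of the planned dose.
- The event review at screening (Appendix 1) covers SAE, CESI, NOCD and MAAE since the parent study ended, not solicited reactions to the parent dose.

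None of these names a prior reaction to ARCT-021.

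**4. How many could be affected.** Five parent cohorts can feed Cohort 1b (SAP 5.2): A (1 µg), B (5 µg), C (10 µg), D1 and D2 (both 7.5 µg). Protocol 2.3 reports no severe or life-threatening solicited events after a single 7.5 µg dose at the first interim, which covers D1 and D2. That leaves 5 − 2 = 3 cohorts with no grade 3 count in the documents. Of these, B had the dose that 2.3 calls similar in safety to 7.5 µg, and A had the lowest dose. C had 10 µg, which 2.3 describes as having the less favourable safety profile. Former Cohort C subjects are therefore the main group of interest, and they would receive a lower dose here (7.5 against 10 µg).

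**The case against.** The strongest reply is that this is an editing fault. If the Table 2 bullets are leftovers, deleting them and correcting the pointers to 8.6 restores consistency. Whether a transient grade 3 reaction should bar one more dose by rule would then be a design preference. Investigators have real discretion under inclusion 4 and exclusions 4 and 14. The number affected may be zero. SAP 4.4 presents Day 29 and Day 57 data for Cohort 1b, which suggests, without proving, that much of the dosing is already done.

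Much of this stands. The leftover reading is the likely one, the discretion is real, and a new exclusion may now reach few subjects. But deletion alone would leave Cohort 1b re-dosed with no contraindication rule, on a rationale that does not describe them.

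Three stronger readings are tempting, and the documents do not support them:
- *Table 2 is an operative bar that Cohort 1b dosing breaches.* Nothing in Table 2 says that a parent-study reaction carries into eligibility here, and its wording most naturally refers to a second injection in this study.
- *The site would not know of the earlier reaction.* Screening does not ask about it again, but 9.4.3 runs these subjects' event recording from the parent dose and 4.1 keeps their parent-study numbers. The gap is in the rule; nothing shows that the information is missing.
- *Subjects with qualifying reactions have been dosed.* The documents give no such case.

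**Conclusion.** The point holds as a gap in the rules for Cohort 1b only. Section 8.6 justifies having no individual stopping rule by a fact that is true of Cohort 1a and untrue of Cohort 1b. Three places point to 8.6 for rules it does not contain. Section 5 leaves a prior reaction to judgement. The clearest uncovered case is a resolved grade 3 solicited reaction to the parent dose.

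Its size is unknown, may be zero, and lies mainly among former 10 µg recipients. This rests on the first-interim statements in 2.3, which give no counts by cohort, and on parent-study data that are not in these documents. The change should be made because it concerns re-exposure and costs little. Confidence is medium, given the probable origin of the Table 2 wording and the partial safeguard of investigator judgement.

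**What to change.** 1. **Section 5.2 and the synopsis list.** For subjects to be dosed here who received ARCT-021 in the parent study, exclude a prior grade 3 solicited AE, anaphylaxis or unexpected systemic hypersensitivity reaction to ARCT-021. Table 2 names grade 3 only. If grade 4 is to be covered, as the contact instruction in 3.8 does, write grade 3 or higher and state that this deliberately broadens Table 2.
2. **Section 8.6.** Limit the single-dose rationale to doses within this study, and refer to the new criterion for earlier doses.
3. **Table 2, 2.6.1, 3.10 and the synopsis.** Correct the two bullets, and point the text to the criterion.
4. **Section 3.2.** Let a seronegative single-dose subject excluded on this ground follow the non-dosed schedule, which is now limited to two-dose and seropositive single-dose subjects. SAE, MAAE and immunogenicity follow-up then continue. CESI reporting continues in any case under 9.5.5.
5. **Look-up.** The interim SAP's Day 29 and Day 57 data show that some Cohort 1b dosing has occurred. Check parent-study reaction data for those subjects, and report any qualifying case.

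The cost is one criterion, wording changes in five places (8.6, Table 2, 2.6.1, 3.10, synopsis), one sentence on the non-dosed schedule, and a look-up made easier by the retained subject numbers. The downside is that a few subjects, possibly none, lose the booster dose.
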